**Protocol Revisions**

Revision Level	Changes made to Protocol	Date	By
0.0	Original Release	October 26, 2015	[name], [name], [name], [name], [name]
1.0	Updated based on IRB comments	November, 03, 2015	[name]
2.0	Updated exclusion and added an additional 30 day take home	January 7, 2016	[name]; [name]
3.0	Updated to include Randomization	January 19, 2016	[name]; [name]
4.0	Updated to include all PSG nights to be randomized	April 08, 2016	[name]; [name]
5.0	Updated based on University of Arizona comments.	April 19, 2016	[name]; [name], [name]
6.0	Added 20 days to complete the PSGs	June 27, 2016	[name]; [name]
7.0	Modified the Incl/Exc. Criteria	November 22, 2016	[name]; [name]

## Glossary of Definitions and Terms

For the purposes of this study, the following definitions will be used.

**Apnea:** The cessation of airflow at the nostrils and mouth for at least 10 seconds as determined using nasal-oral thermistor or device flow.

**Apnea/Hypopnea Index (AHI):** The number of apneas and hypopneas per hour of sleep.

**Auto Adjusting Continuous Positive Airway Pressure Device:** A type of CPAP machine that monitors changes in breathing and compensates automatically by making appropriate therapeutic adjustments in pressure delivery.

**Bi-Level PAP Therapy:** Responds to both inspiration and expiration by the patient and delivers a set amount of pressure when the patient begins spontaneous inhalation and decreasing pressure when exhalation begins.

**Central Apnea:** The cessation of airflow at the nostrils and mouth for at least 10 seconds that is associated with the absence of inspiratory effort.

**Central Apnea Index (CAI):** The number of central apneas divided by the number of hours of sleep.

**Complex Sleep Apnea Syndrome (Comp SAS):** Presence of any of the following sleep disordered breathing conditions, independently or in any combination: Periodic Breathing including Central Sleep Apnea (CSA), Cheyne Stokes Respiration (CSR), and / or CPAP emergent central sleep apnea.

**Compliance:** Adhering to or conforming to a regimen of treatment such as CPAP or Bi-Level PAP.

**CPAP Pressure:** Prescribed therapeutic pressure needed to maintain an open airway in a sleep apnea patient treated with CPAP, expressed in centimeters of water (cm H2O). The positive pressure can range from 4 - 25 cm H2O. Different patients require different pressures. The needed therapeutic pressure is determined in a CPAP titration study.

**CPAP Therapy:** Continuous Positive Airway Pressure – delivers a constant pressure during inspiration and expiration.

**EPAP:** Expiratory Positive Airway Pressure - prescribed pressure for the expiratory (breathing out) phase of an individual on Bi-level PAP therapy.

**Hyper somnolence:** Excessive daytime sleepiness.

**Hypopnea:** Shallow breathing in which the air flow in and out of the airway is significantly reduced as detected by nasal pressure or device flow - often associated with oxygen desaturation of 4% or EEG arousal.

**IPAP:** Inspiratory Positive Airway Pressure - Physician prescribed pressure for the inspiratory (breathing in) phase of an individual on Bi-level PAP therapy.

**EAP:** End Expiratory Pressure, the pressure applied at patient mask during end of expiration.

**OSAHS:** Obstructive Sleep Apnea Hypopnea Syndrome- a disorder in which complete or partial obstruction of the airway (apneas or hypopneas) during sleep causes loud snoring, oxyhemoglobin desaturations and frequent arousals.

**Polysomnography (PSG):** Continuous and simultaneous recording of physiological variables during sleep, i.e., EEG, EOG, EMG (the three basic stage scoring parameters), EKG, respiratory air flow, respiratory excursion, lower limb movement, and other electrophysiological variables. 

## **I. Background and Significance**

Obstructive Sleep Apnea-Hypopnea Syndrome (OSAHS) is a condition characterized by intermittent partial collapse and closure of the upper airway (UA). The partial collapse and closure of the airway leads to sleep fragmentation, oxygen desaturation, hypercarbia, and activation of the sympathetic nervous system. A result of disrupted sleep may be excessive daytime sleepiness. The syndrome is also associated with behavioral, functional, cardiovascular and cognitive dysfunction. (2, 3, 4)

Continuous Positive Airway Pressure (CPAP) is the most effective treatment for the OSAHS. CPAP stabilizes the airway and prevents instability and collapse. With a stable and patent airway, breathing continues in a normal manner, gas exchange is improved, and there is no disruption of sleep related to disturbed breathing. (5)

CPAP is applied to the upper airway via a mask that covers the nose or the nose and mouth and reduces or eliminates sleep disordered breathing. The period of maximum susceptibility to airway collapse is at the end of exhalation and during early inhalation. During inhalation, negative pressures are generated in the airway by the normal process of ventilation (increase of thoracic volume and reduction of intra-thoracic pressure). The constant pressure of CPAP supports the airway throughout the ventilatory cycle. (3)

In the sleep laboratory, manual titration of positive airway pressure is performed to determine effective CPAP pressures. During the in-lab procedure, the patient is instrumented for full polysomnography (PSG). Therapy is applied and pressure is adjusted during the course of the night to stabilize the upper airway and the breathing pattern. With conventional CPAP, a single pressure level is applied to the airway. While adequate for a majority of patients with obstructive sleep apnea, this static prescription will present challenges in certain patients and conditions. (6 7)

Other forms of positive airway pressure that are approved for the treatment of OSAHS include automatically adjusting CPAP, Bi-level Positive Airway Pressure (BiPAP), and automatically adjusting BiPAP. Automatically adjusting CPAP (Auto CPAP) evaluates the airflow pattern and adjusts pressure to optimize airflow. Pressure is increased or decreased at specific time intervals to adjust therapy in a proactive fashion. Auto CPAP accommodates patients presenting with highly variable pressure requirements (e.g., sleep stage or body position dependent sleep apnea). The automatic adjustment can be used in patients for whom in-laboratory therapy titration is either delayed or impossible. (8, 9, 10)

The REMStar Auto algorithm is a pro-active, flow-based algorithm. The basic algorithm evaluates the inspiratory flow and determines impending or actual flow limitation. This multi-dimensional flow evaluation occurs in concert with a program of pressure adjustments designed to evaluate the critical pressures (pressure at which the airway is susceptible to collapse) and maintains pressures slightly above the critical pressure. The patient is protected from “break-through” events with a full complement of intelligent responses to airflow events and snoring. (1)

BiPAP therapy is an alternative to CPAP therapy. With BiPAP therapy, the patient’s breathing pattern is monitored to identify the inspiratory and expiratory phases. Pressure is increased during inhalation and returned to a lower pressure during exhalation. Although titration procedures vary, the expiratory pressure (expiratory positive airway pressure or EPAP) is adjusted to prevent airway collapse (apnea) and the inspiratory pressure (inspiratory positive airway pressure or IPAP) is adjusted to prevent airflow limitation, hypopnea, snoring or arterial desaturation not associated with complete airway obstruction. BiPAP therapy differs from CPAP therapy, in that in addition to stabilizing the airway, inspiratory effort

is assisted by the difference between the inspiratory and expiratory pressure. This difference between EPAP and IPAP pressures is often referred to as “Pressure Support”. (1, 3, 8, 10)

Patients with OSAHS may be prescribed BiPAP therapy if CPAP therapy is not tolerated. BiPAP therapy may also be prescribed for patients with other respiratory disorders or for patients with both sleep related airway instability and impaired lung function.

Automatically adjusted Bi-Level Positive Airway Pressure (Auto BiPAP®) is currently marketed for the treatment of OSAHS. Auto BiPAP adjusts EPAP levels based upon the detection of an apnea or evidence of airway instability. IPAP is adjusted to overcome hypopnea and airflow limitation.

Patients experiencing reduced ventilation from lung disease, neuromuscular disorders, or problems with the control of the breathing can experience nocturnal hypoventilation that is worse during sleep than it is during wakefulness. These patients are typically more complex and require more extensive evaluation and follow-up than patients suffering only from OSAHS. Patients may also be more vulnerable to loss or interruptions in treatment and often require more advanced modes and features such as alarms and timed back-up breaths.

OSAHS patients may respond to increases in CPAP or BiPAP therapy by demonstrating a shift in the nature of the apnea from obstructive to central. In these cases, patients may not receive adequate treatment with CPAP since lower pressure levels do not manage the instability of the airway leaving residual airway obstruction, while higher pressure levels are associated with CPAP emergent events. This condition is referred to as CPAP Emergent Complex Apnea.

Auto SV (Auto Servo Ventilation) is a mode of positive airway pressure used to treat obstructive and complex central sleep apnea. The main features of the Auto SV mode include:

- Normalization of ventilation by automatically adjusting IPAP pressure to achieve a target ventilation. IPAP is increased or decreased to help stabilize the ventilation.
- Provision of timed, back-up breaths during central apneas. The optimal back-up rate is automatically determined by the device based on the patient’s breathing.
- Automatic control of EPAP pressure to treat obstructive events.

Several manufacturers produce these types of devices. The algorithms used to determine the IPAP, EPAP and minimum respiratory rate are different. The largest number of these devices currently in use are the BiPAP AutoSV Advanced System One (Philips Respironics, Murrysville PA) and the VPAP Adapt (ResMed Corp., San Diego CA).

## **I. Purpose and Scope**

This study is to better understand the performance and features of the BiPAP autoSV Advanced System One. Philips Respironics will evaluate the PSG and Encore data from each night. The aim of the study is to characterize the acute outcomes of treatment provided by the device and evaluate any modifications made to the Philips Respironics device’s algorithm

The participants for this study will be experienced in having used servo ventilation therapy at their home because it is only such patients who are already using servo ventilation as part of routine clinical care that are eligible for participation.

Participants will receive four (4) randomized PSG's during which they will receive treatment from the following devices in a randomized manner:

- FDA released Philips BiPAP AutoSV Advanced System One
- A Modified Philips BiPAP ASV
- FDA released ResMed S7 VPAP Adapt
- FDA released ResMed S9 VPAP Adapt

### **Target Patient Population**

The participants sought for this effort will be previously prescribed a servo-ventilation device as part of routine clinical care.

## **II. Study Objective**

The objective of this study is to compare the performance of servo ventilation devices.

## **III. Participant Selection**

Participants will be recruited from the sleep center laboratory, clinics, through recruitment flyers as well as through IRB approved PHI waiver aimed at soliciting potential participants to enroll in the study. Eligible participants will be required to provide informed consent prior to beginning their participation in this study.

The inclusion and exclusion criteria for this study are listed below. All participants are required to demonstrate Sleep Disordered Breathing conditions requiring treatment with a servo-ventilation device.

### **Inclusion Criteria**

- Ability to provide consent
- Age  $\geq$  21
- Currently prescribed servo ventilation therapy at home
- Current device compliance report demonstrating residual AHI of 4 or more

### **Exclusion Criteria**

- Participants who are acutely ill, medically complicated or who are medically unstable
- Participants in whom PAP therapy is otherwise medically contraindicated
- Participants who are claustrophobic
- Symptomatic ("Symptomatic" defined as hospitalized for heart failure or a change in cardiac medications, within the last two months) chronic heart failure (NYHA 2-4) and reduced LVEF $\leq$ 45%, AND moderate to severe predominant central sleep apnea
- Participants with previously diagnosed respiratory failure or respiratory insufficiency and who are known to have elevated arterial carbon dioxide levels while awake (PaCO2  $\geq$  55mmHg).
- Participants requiring any kind of oxygen therapy
- Participants who have had surgery of the upper airway, nose, sinus, eyes, or middle ear within the previous 90 days
- Participants with untreated, non-OSA sleep disorders, including but not limited to; insomnia, periodic limb movement syndrome, or restless legs syndrome (PLMI > 15).

**V. Participant Enrollment**

**Sample Size:** This is a pilot study and no formal sample size calculation has been performed. Up to fifty (50) participants may be screened for this study with the intent on collecting data from forty (40) participants.

**Table 1. Study Procedures**

Baseline with PSG
 
 
• Informed Consent
 
• Inclusion/Exclusion Criteria Review
 
• Demographics
 
• Anthropometric Measurements
 
• PAP Prescription information (if available; from Device or from Medical records). This is the pressure settings of the device that was prescribed by the patient’s clinical sleep medicine provider.
 
• Medical History and physical examination
 
• Sleep History- Including that past 30 day detailed report
 
• Diagnostic PSG history (copies of sleep studies that were performed as part of routine clinical care in the past that qualified the patient for the servo-ventilation device)
 
• Current Medications
 
• Vital Signs (at beginning of PSG night)
 
• Research Trial PSG- Randomized to a device
 

Procedures for Each PSG after Baseline
 
 
• Current Medications
 
• Vital Signs (at beginning of PSG night)
 
• Research Trial PSG- Randomized to one of the four devices (4 research PSGs will be performed for each subject over a 20 day period).
 

30 day Take Home with Modified Philips BiPAP ASV device
 
After the last PSG participants will be sent home on Modified Philips ASV study device. A wireless modem will be connected to the Modified Philips ASV study device. The wireless modem is for device data collection/transmission purposes only that monitors the usage and performance of the device in the home-setting.
 
The device setting should be set to the following:  P max: 30  EPAP min: 4  EPAPmax:15  PS min: 0  PS max: 15  BiFlex: 2  Rate: Auto

After 30 day Take Home Participants Will
 
 
• Return to the Sleep Lab
 
• Complete the end of study questionnaire
 
• Return all of the study equipment
 

**Additional Take Home with the Modified Philips BiPAP ASV device:**

- Participants may be asked to use the Modified Philips ASV study device for an additional 30 days if more data is needed for analysis. Participants will complete the same end of day questionnaire noted above.

**After trial completion:**

- When the Participant is done with the trial they will go back to using their own prescribed device.

Polysomnography

For each PSG, participants will be asked to report to the sleep center and/or research site at a predetermined time agreeable to the participant and the sleep center. The participant may be asked to return for up to four sleep studies, as described above.

During the PSG, participants will use their own mask and accessories from their home treatment in order to maximize their comfort. Should the participant need a mask or should the sleep technologist feel the mask is not appropriate for the PSG, the participant will be provided a new mask as part of this study by the research site.

Participants will be instrumented for PSG via sleep acquisition system. The PSG will be configured per standard operating procedures at the research site.

- Two belts secured around the chest and abdomen to measure movements associated with breathing effort
- A small sensor which attaches to the chest belt to measure body position
- Electroencephalographic (EEG) leads attached to the scalp and face to measure sleep stages (F4-M1/A1, C4-M1/A1, O2-M1/A1, F3-M2/A2, C3-M2/A2, O1-M2/A2), left and right electro-oculograms, submental and frontal electromyogram, respiratory effort, oximetry, and right and left anterior tibialis electromyogram (11).
- A flexible finger sensor placed on the finger to measure arterial saturation (SpO2)
- Surface electrodes attached to the skin bilaterally over the anterior tibialis muscle, to measure leg movements
- A microphone attached to the skin at the base of the neck to measure snoring sounds. The microphone is no bigger than a nickel.
- A plethysmography signal from the pulse oximetry device may be added to the montage
- Lead II ECG Electrode derivation
- Several channels of data (flow, pressure, and other device generated information) from each therapy device will be included as part of the PSG montage:

Participants will be monitored closely by a trained sleep technologist during each PSG.

**Randomized PSG Device Set Up:**

**Philips BiPAP ASV PSG Set Up**

The following device settings will be set up for the PSG night:

- FDA released Philips BiPAP AutoSV Advanced System One
- The modified Philips BiPAP ASV

P max: 30  
EPAP min: 4  
EPAPmax: 15  
PS min: 0  
PS max: 15  
BiFlex: 2  
Rate: Auto

**ResMed BiPAP ASV PSG Set Up**

The ResMed devices noted below will be configured to operate on the following device settings for the PSG night:

- FDA released ResMed S7 (VPAP Adapt SV)

EEP: 4  
PSmin: 3  
PSMax: 16

- FDA released ResMed S9 (S9 VPAP Adapt)

EPAP min: 4  
EPAPmax: 15  
PS min: 0  
PS max: 20  
Max Ramp: Off

If the device is not adequately treating the participant, the device may be adjusted during the night. If available, device data normally stored on internal memory or written on to a data card in the device will be collected and reviewed for each PSG.

All PSG's will be scored using Somnolyzer automated scoring software to determine all sleep and respiratory parameters. Results of the PSG's will not be used to make any decisions or recommendations on the participant's usual treatment.

**VI. Statistical Analysis**

Baseline data will be presented with descriptive statistics. Endpoints will be compared between therapy nights, and between device and PSG scores. Data that are not normally distributed may undergo appropriate transformation to fit the assumptions of a paired t-test. Otherwise, the nonparametric

Wilcoxon Signed Rank test will be used. All tests will be conducted at a significance level of  $p < 0.05$ , and confidence intervals will be presented.

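### For device versus PSG scores the plan names only paired location tests, which address average bias but not how far a single device score lies from the same night's PSG score

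*Combined protocol and SAP*

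**What the plan says.** Section VI (Statistical Analysis) is the only statistical section. It announces two comparisons in one sentence: "Endpoints will be compared between therapy nights, and between device and PSG scores". One set of methods then follows for both. "Data that are not normally distributed may undergo appropriate transformation to fit the assumptions of a paired t-test"; otherwise the Wilcoxon signed-rank test is used. All tests are at p < 0.05, and "confidence intervals will be presented", without saying for which quantity.

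The two scores come from the same night. PSGs "will be scored using Somnolyzer automated scoring software" (ResMed BiPAP ASV PSG Set Up). The same section covers the device side, for each PSG: "If available, device data normally stored on internal memory or written on to a data card in the device will be collected and reviewed".

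The documents name no limits of agreement, concordance or intraclass correlation, or SD of device-minus-PSG differences. Section V gives a target of 40 participants with data and states that this is a pilot without a formal sample size calculation.

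**The concern.** Two therapy nights are two conditions, and asking whether the outcome shifts on average between them is the right question. Device and PSG scores are two readings of one night. Average bias is a fair question there too, but not the whole one: over-readings in some participants and under-readings in others can cancel in the mean. A paired t-test or signed-rank test then finds nothing, however large the individual errors are, and a reader may take that as agreement.

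What is at stake is how much the study can say about single device scores. The Modified Philips device is the clearest case: "After the last PSG participants will be sent home on Modified Philips ASV study device", and Table 1 lists no PSG during the home period. Any breathing index from that period would therefore be device-scored, and the PSG nights are the only place in the study where such a score can be set against PSG.

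**Working it through.** The plan has no figure to reproduce, because it gives no effect size, SD or power. The check therefore asks how the named tests behave as individual agreement worsens.

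**Inputs**
- n = 40 pairs per device: the target in section V. Fewer are possible, since device data are collected only where available; n = 20 and n = 30 are shown for some results.
- Two-sided 0.05: the level is from section VI; two-sidedness is assumed.
- Index: AHI in events/h, as an example. Section VI names no index.
- Bias 0 or 1/h and SD of differences 2, 5 or 8/h, with normal differences: all assumed.
- A difference of 4/h as a yardstick: illustrative, not a tolerance.

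**Formulas**
- Half-width of the 95% CI for the mean difference: t(0.975, n−1) × SD/√n. At n = 40 this is 2.023 × SD/6.325 = 0.320 SD.
- 95% limits of agreement: bias ± 1.96 SD.
- Share of participants beyond 4/h: Φ((−4 − bias)/SD) + 1 − Φ((4 − bias)/SD).
- Chance of a significant t-test: noncentral t with n−1 df and noncentrality bias × √n/SD.

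**Zero bias, n = 40**

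| SD (/h) | Non-significant | CI half-width, mean (/h) | Limits of agreement (/h) | Beyond 4/h |
|---|---|---|---|---|
| 2 | 95% | 0.64 | ±3.9 | 5% |
| 5 | 95% | 1.60 | ±9.8 | 42% |
| 8 | 95% | 2.56 | ±15.7 | 62% |

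The rejection rate is 5% at every SD, because the null hypothesis of no average shift is true. The Wilcoxon test behaves alike: in 8,000 simulations it rejected in 0.050, 0.050 and 0.048.

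**Bias 1/h, n = 40**

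| SD (/h) | Noncentrality | Significant (t) | Significant (Wilcoxon, simulated) | Limits of agreement (/h) | Beyond 4/h |
|---|---|---|---|---|---|
| 2 | 3.16 | 87% | 86% | −2.9 to 4.9 | 7% |
| 5 | 1.26 | 23% | 22% | −8.8 to 10.8 | 43% |
| 8 | 0.79 | 12% | 12% | −14.7 to 16.7 | 62% |

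At this non-zero bias, greater scatter makes a significant result less likely. At n = 20 the t-test figures are 56%, 14% and 8%.

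**The opposite case.** With bias 0.5/h and SD 0.5/h at n = 40, the t-test is significant more than 99.9% of the time, although the limits are only 0.5 ± 0.98, that is −0.5 to 1.5/h. The p-value can mislead in either direction.

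**Do the promised intervals fill the gap?** Beside these tests they would naturally be intervals for a mean or median difference. At n = 40 the limits of agreement are 1.96/0.320 = 6.1 times as wide as the t interval. A reader could recover the SD from a t interval on the raw scale together with n, but the plan commits to neither, and the Wilcoxon route does not allow it.

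**Precision of the added limits.** The approximate 95% half-width of each limit, in SD units, is t × √(1/n + 1.96²/(2(n−1))). At n = 40: 2.023 × √(0.0250 + 0.0493) = 0.55. At n = 30: 0.65. At n = 20: 0.81.

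**The case against.** The strongest reply is that the plan claims no more than it tests. Section VI says only that scores will be compared, and the objective in section II is to compare the performance of the devices. The named tests do answer whether device and PSG scores differ on average. All of this stands. A reader might infer that the plan means to show device scores to be interchangeable with PSG, or to validate them; no section says so, and the misreading of a null result is a risk, not something the plan asserts.

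A reader might also infer that the home phase rests on this comparison. Table 1 says of the modem: "The wireless modem is for device data collection/transmission purposes only that monitors the usage and performance of the device in the home-setting". The phase may be extended "for an additional 30 days if more data is needed for analysis". Neither statement names a breathing index or an analysis, and section VI names no home-phase endpoint. That device-scored home data will carry a conclusion is therefore an inference.

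Two further limits are fair. The bias and SD values are assumed, so the documents cannot show whether individual disagreement here would be small or large. And the statement that worse agreement is less likely to be flagged does not hold in general: at zero bias the rejection rate stays at 5% whatever the SD. It holds only for a given non-zero bias.

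Pilot status does not remove the point. It explains why there is no sample size calculation, not why a planned comparison should report location alone. That the spread could be computed afterwards from the same pairs is true; it makes the change cheap, but the plan does not commit to doing it.

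**Conclusion.** The point holds as a minor one. For device versus PSG, the plan commits only to methods that address average bias; it does not commit to reporting individual departures, and a non-significant test is not evidence of agreement. That conclusion follows from the text and does not depend on the assumed figures.

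The size is illustrative. With 40 pairs, normal differences and zero bias, the same 95% chance of a non-significant result goes with limits of agreement anywhere from ±3.9 to ±15.7/h as the SD goes from 2 to 8/h.

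The comparison is secondary, the study is a pilot, and no stated conclusion, at home or in the laboratory, depends on it. The paired tests for therapy nights are not in question.

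**What to change.** Keep the paired tests for therapy nights. For device versus PSG, add to section VI that the following will be reported for each device, using one pair per participant:
- the number of pairs, since device data may be missing;
- the mean difference with its 95% CI;
- the SD of the differences;
- Bland-Altman 95% limits of agreement with CIs, on a suitable scale if the spread grows with the score.

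State that the limits are descriptive and are relative to Somnolyzer-scored PSG. The score being compared has to be named for this to be usable.

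The cost is a few sentences and slightly more analysis on data already planned, with no added participants or visits. The drawback is precision: each limit carries about ±0.55 SD with 40 pairs and ±0.81 SD with 20, so the limits should be read with their intervals.
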